#### **6.7 General Concomitant Medication and Supportive Care Guidelines**

In general, concomitant medications and therapies deemed necessary for the supportive

care and safety of the subject are allowed, provided their use is documented in the medical records. Local vaccine site reaction may be treated with topical applications of aloe vera or vitamin E gel or lotion. Significant local inflammation that is causing the research participant severe pain or is interfering with the activities of daily living may be treated with cold packs and oral analgesics. Local toxicities of pruritus at the vaccine sites and systemic pruritus may be treated with topical or oral diphenhydramine hydrochloride (Benadryl) or topical aloe vera. If oral diphenhydramine hydrochloride is used the recommended dose shall be 25-50 mg every four to six hours as needed for pruritus, not to exceed 300 mg/day. Severe local inflammation or significant clinical autoimmunity will be managed on a case by case basis.

Use the following medications are prohibited during the vaccination administration period and one month (28 days) after last vaccination received:

- Any non-study anticancer or immunotherapy agent (investigational or non-investigational)
- Any other investigational agents
- Live vaccines (examples of live vaccines include, but are not limited to: measles, mumps, rubella, chicken pox, yellow fever, rabies, BCG, and typhoid [oral] vaccine). Seasonal influenza vaccines for injection are generally killed virus vaccines and are allowed. However, intranasal influenza vaccines (e.g. Flu-Mist®) are live attenuated vaccines, and are not allowed.

All concomitant medications will be reviewed and recorded by study staff during the study.

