#### **6.5 Dose Modifications and Delays**

Dose reduction or dose increase of TA-CIN will not be permitted. The dose in this study is fixed.

In the event that TA-CIN re-treatment criteria are not met, treatment may be delayed for up to 14 days. Future doses should be delayed accordingly such that at least 23 days is maintained between each dose of TA-CIN. The timing for the Month 6, 12, and 24 assessments should be scheduled from the initial dose of TA-CIN.

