## **6.9 Duration of Therapy**

In the absence of treatment delays due to adverse event(s), treatment may continue for a total of three vaccinations or until one of the following criteria applies:

- Disease recurrence,
- Intercurrent illness that prevents further administration of treatment,
- Unacceptable adverse event(s) (**Section 6.6**),
- Patient or legal representative withdraws consent from the study,
- Patient is lost to follow-up,
- General or specific changes in the patient's condition render the patient unacceptable for further treatment in the judgment of the investigator,
- Non-compliance with protocol or treatment,

- Use of systemic glucocorticoids or other immune-suppressive drugs for more than 7 days required at any time after enrollment in the study, or
- Termination of the study.

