#### **6.10 Duration of Follow-Up**

Patients will be followed for 24 months after initiation of study treatment or until death, whichever occurs first. Patients who are discontinued from the study treatment due to an unacceptable drug-related AE will be monitored for safety until the resolution of the AE to  $\leq$  grade 1 or stabilization or until initiation of a new therapy for their cancer, whichever occurs first.

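### Section 6.7 bans anticancer agents with no exception for recurrence, and Section 12.1 counts a rise first seen after new cancer therapy as a vaccine response; the effect on site selection is small

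*Combined protocol and SAP*

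**What the plan says.** **Treatment ban.** Section 6.7 names classes of agent that are "prohibited during the vaccination administration period and one month (28 days) after last vaccination received". One item begins "Any non-study anticancer or immunotherapy agent (investigational or non-investigational"; another is "Any other investigational agents". The clock runs from the last dose actually given. The section opens by allowing therapies needed for supportive care and safety, and it ends: "All concomitant medications will be reviewed and recorded by study staff during the study".

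**Recurrence.** Under Section 6.9, "treatment may continue for a total of three vaccinations or until one of the following criteria applies", and recurrence is the first criterion listed. Nothing there refers back to the ban. Section 6.10 adds: "Patients will be followed for 24 months after initiation of study treatment or until death, whichever occurs first". It mentions new cancer treatment once, where safety monitoring after an unacceptable drug-related event runs to resolution or stabilization "or until initiation of a new therapy for their cancer".

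**Response rule.** Section 12.1 calls a patient a responder if her largest rise after TA-CIN, in T cell number or proliferation index, exceeds 1.8 baseline SDs and is at least 2-fold. The endpoint is read at the fourth follow-up measurement. In the Section 10 calendar the T cell draws after the first dose are at Week 5, Week 9, Week 11-13 and Months 6, 12 and 24, so the fourth is Month 6. Section 12.5 speaks of five post-treatment time points, which would add Month 12. Neither section excludes or flags a sample taken after recurrence or new therapy. Section 12.5 picks the site on the observed number of responses.

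**The concern.** These are two separate gaps that arise from the same event, a recurrence.

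The first concerns care. A patient whose cancer returns during dosing, or within 28 days of her last dose, stops TA-CIN but remains under a ban that covers non-investigational drugs. A site that follows the text must delay systemic therapy or record a deviation. Surgery and radiation are not expressly barred.

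The second concerns attribution. The ban lapses before Month 6 while sampling continues, so a patient who has not responded to TA-CIN may start chemotherapy, immunotherapy or radiation and first meet the response rule afterwards. She is then counted for her injection site. Section 12.2 itself expects earlier chemo/radiotherapy to raise the T cell response, so the plan cannot treat such a rise as due to the site alone. With about 7 patients per group and a choice made on counts, one patient can make or break a tie. A patient who met the rule before the new therapy is unaffected.

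**Working it through.** **Length of the hold.** Hold = 28 minus days since the last dose, not below 0.
- Dosing visit, before the dose: 28 days since the last dose gives 0. Section 6.5 lets doses move "such that at least 23 days is maintained between each dose of TA-CIN", and 28 - 23 = 5. Range 0 to 5 days.
- Week 11-13 visit (Days 71 to 91) with dose 3 on Day 57: 14 to 34 days since dose, so the hold is 14 to 0 days.
- Recurrence found just after a dose: up to 28 days.

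**Which samples are exposed.** On schedule the ban ends on Day 57 + 28 = 85. Month 6 is Day 183 ± 28, or Days 155 to 211. If doses 2 and 3 each slip 14 days, the last dose is Day 85 and the ban ends on Day 113, still before Month 6. If dosing stops after dose 1, the ban ends on Day 29 and the Week 9 and Week 11-13 samples are exposed too. Radiation could precede any later draw. Exposure is therefore mainly at Month 6 and after, but not only there.

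**The plan's own figure.** Section 12.2 takes 7 per group and response rates of 65% (Group A, thigh) vs 45% (Group B, arm), or 60% vs 45%. With independent binomial counts, P(A > B), not counting ties as correct, is 69.3% and 62.1%. The plan states about 70% and about 60%.

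**Effect on a correct pick.** The documents give no recurrence rate. Assume r = 10%, 20% or 40% by 24 months (730 days) at constant hazard, the same in both groups. Assume also that every non-responder who recurs by Day 182 is treated, sampled and converted. Then

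q = 1 - (1 - r)^(182/730) = 2.6%, 5.4%, 12.0%,

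and each true rate p becomes p + (1 - p)q. For r = 40%, 65% becomes 0.65 + 0.35 × 0.120 = 69.2%, and 45% becomes 0.45 + 0.55 × 0.120 = 51.6%. Recomputing P(A > B):

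| Recurrence by 24 months | 65% vs 45% | 60% vs 45% |
|---|---|---|
| none | 69.3% | 62.1% |
| 10% | 68.7% | 61.6% |
| 20% | 67.9% | 61.0% |
| 40% | 66.2% | 59.6% |

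The loss is 0.6 to 3.1 percentage points.

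**Any change in the comparison.** Under the same model, the sign of the difference between sites changes in 4.9%, 9.3% and 17.0% of trials (65% vs 45%) or 5.7%, 10.8% and 19.4% (60% vs 45%). Nearly all of these are ties made or broken, in either direction. The winner reverses in 0.1-1.5% or 0.1-1.8%.

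**End of the Month 6 window.** Running the model to Day 211 at 40% recurrence, the comparison changes in 18.7% and 21.1% of trials and the winner reverses in 1.8% and 2.2%. The Day 182 figures are therefore not upper limits.

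**The case against.** **On the ban.** Entry requires no evidence of recurrence within 8 weeks of enrollment, and the calendar schedules no scan after baseline, so a recurrence found before about Day 85 should be uncommon. Section 6.9 stops the vaccine, a patient may withdraw consent, Section 6.10 mentions new cancer therapy without a waiting period, and Section 6.7 opens with a general allowance for safety. A reader might infer that the protocol sets out to withhold treatment from relapsed patients. The documents do not support that: the conflict arises from a literal reading and lasts 28 days at most. It still stands as a drafting gap, because the specific ban names non-investigational agents and nothing lifts it.

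**On the analysis.** A reader might infer that site selection is seriously unreliable, because one converted non-responder changes the comparison in 33.5% (in Group A) or 32.2% (in Group B) of trials at 65% vs 45%, and in 36.8% or 36.3% at 60% vs 45%. Those figures assume that the conversion has already happened, and they count ties moved in favour of the truly better site. The design aims at a correct pick, and that chance moves little.

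Nor do the documents show that therapy given after vaccination produces a qualifying rise. Section 12.2 speaks only of therapy given before it, so 100% conversion is an assumption. Individual time-course plots and recorded drugs would let the team see a late rise in about 15 patients, and Section 1 also weighs toxicity and fallback assays. All of this stands and limits the size of the point. It does not supply the missing rule.

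**Conclusion.** Both gaps are real and small, and neither adds weight to the other. Followed as written, Section 6.7 holds systemic treatment of a recurrence for up to 28 days or produces a deviation; at the scheduled visits examined above the hold is much shorter. Section 12.1 credits the injection site with any qualifying rise, including one first seen after new cancer therapy. The cost to a correct pick is 0.6 to 3.1 points.

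That range rests on an assumed 10-40% recurrence at constant hazard, equal in both groups, with every recurring non-responder converted by Day 182. Full conversion makes the effect larger. Stopping at Day 182 makes it smaller, since the Month 6 window runs to Day 211 and Section 12.5 may bring in Month 12. The figures are scenarios, not bounds.

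**What to change.** Add to Section 6.7: *The prohibitions on anticancer and other investigational agents end when TA-CIN is permanently discontinued for disease recurrence.*

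Add to Section 12.5: *Immune response is classified from samples drawn before the start of any new anticancer therapy, including radiation; the number of patients affected is reported by injection site, and the selection is repeated with their later samples included.*

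Record the start date of any radiation given for recurrence. Drugs are already recorded under Section 6.7.

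The cost is two sentences and one recorded date, with no extra patients, visits or samples. The downside is small: a true vaccine response that first appears after new therapy is missed in the main classification, but the repeated selection shows it.

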## **6.8 Contraception, Use in Pregnancy, Use in Nursing**

TA-CIN may have adverse effects on an embryo or fetus; therefore, women of childbearing potential with fertility sparing procedures will not be eligible for enrollment.

## **6.9 Duration of Therapy**

In the absence of treatment delays due to adverse event(s), treatment may continue for a total of three vaccinations or until one of the following criteria applies:

- Disease recurrence,
- Intercurrent illness that prevents further administration of treatment,
- Unacceptable adverse event(s) (**Section 6.6**),
- Patient or legal representative withdraws consent from the study,
- Patient is lost to follow-up,
- General or specific changes in the patient's condition render the patient unacceptable for further treatment in the judgment of the investigator,
- Non-compliance with protocol or treatment,

- Use of systemic glucocorticoids or other immune-suppressive drugs for more than 7 days required at any time after enrollment in the study, or
- Termination of the study.

#### **6.10 Duration of Follow-Up**

Patients will be followed for 24 months after initiation of study treatment or until death, whichever occurs first. Patients who are discontinued from the study treatment due to an unacceptable drug-related AE will be monitored for safety until the resolution of the AE to  $\leq$  grade 1 or stabilization or until initiation of a new therapy for their cancer, whichever occurs first.

### **7. ADVERSE EVENTS**

This study will use the descriptions and grading scales found in the revised National Cancer Institute Common Terminology Criteria for Adverse Events (CTCAE) Version 4.0 for adverse event reporting that can be found at [http://ctep.cancer.gov/protocolDevelopment/electronic\\_applications/ctc.htm](http://ctep.cancer.gov/protocolDevelopment/electronic_applications/ctc.htm).

Information about all adverse events, whether volunteered by the subject, discovered by investigator questioning, or detected through physical examination, laboratory test or other means, will be collected, recorded, and followed as appropriate.

All adverse events experienced by subjects will be collected and reported from the time of consent, throughout the study, and will only be followed until month 24 unless related to the investigational vaccine. All adverse events related to the vaccine will be followed until resolution.

Subjects who have an ongoing adverse event related to the study procedures and/or medication(s) may continue to be periodically contacted by a member of the study staff until the event is resolved or determined to be irreversible by the investigator.

**Laboratory abnormalities:** Laboratory abnormalities present at the screening visit will be recorded as pre-treatment signs and symptoms. After study treatment administration, all grade 3 and 4 clinical laboratory results that represent an increase in severity from baseline (pre-study) will be reported as adverse events. A grade 1 or 2 clinical laboratory abnormality should be reported as an adverse event only if it is considered clinically significant by the investigator.

**Vaccination site assessment:** This study will use the CTCAE version 4.0 injection site reaction grading scale as it relates to vaccine administration associated adverse events. Patients are to have the site of vaccination examined for pain, erythema, warmth, pruritis, induration/fibrosis, and bruising. A follow-up phone call will be made to the patient 7 days after receiving the vaccine to obtain a self-assessment of the vaccination site. The vaccine site(s) will be assessed by the research nurse (or designated clinician) at each subsequent vaccination visit (Day 1 on Weeks 5 and 9) and at the follow-up visit between Weeks 11-13.

for local reactions. An optional skin biopsy and/or photographs may be obtained based on the assessment by the principal investigator if the subject has a systemic rash, or an unusual vaccine reaction. In addition to sending this to pathology for diagnosis, we will use additional material from the biopsy for research purposes to understand the effects of the vaccine. We will follow these local reactions until complete resolution.

## 7.1 Definitions

### 7.1.1 Adverse Event (AE)

Adverse event is defined as any undesirable sign, symptom or medical condition occurring after starting the study drug (or therapy) even if the event is not considered to be related to the study. An undesirable medical condition can be symptoms (e.g., nausea, chest pain), signs (e.g., tachycardia, enlarged liver) or the abnormal results of an investigation (e.g., laboratory findings, electrocardiogram).

Medical conditions/diseases present before starting the study treatment are only considered adverse events if they worsen after starting the study treatment (any procedures specified in the protocol). Adverse events occurring before starting the study treatment but after signing the informed consent form will be recorded.

Abnormal laboratory values or test results constitute adverse events only if they induce clinical signs or symptoms or require therapy.

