#### **6.4 Re-Treatment Criteria**

Subjects must maintain the following in order to receive each additional dose of study medication:

• ECOG performance status	0 - 1
• white blood cell count	$\geq 3,000$
• lymphocyte number	$\geq 500$
• absolute neutrophil count	$\geq 1,000$
• platelets	$\geq 90,000$
• hemoglobin	$\geq 9$
• total bilirubin	$<1.5 \times$ upper limit of normal (ULN) ( $<3 \times$ ULN if Gilbert's disease)
• AST(SGOT)/ALT(SGPT)	$<3 \times$ ULN
• creatinine	$<1.5 \times$ ULN or estimated creatinine clearance $\geq 60$ ml/min per Modified Cockcroft-Gault Formula

In addition, subjects must not have any acute grade 3 or higher hematologic and/or non-hematological adverse event that is judged possibly, probably or definitely related to the investigational drug agent and/or administration occurring on or after the first day of vaccine administration.

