#### **6.6 Unacceptable Toxicity and Early Stopping Rules**

Unacceptable toxicities are defined as treatment-related  $\geq$  grade 4 AEs, or treatment-related grade 3 AEs not improving to  $\leq$  grade 2 under therapy within 2 weeks. Exceptions include: Grade 3 lymphopenia. Because this is a pilot study evaluating safety of immunization, the stopping rule for safety is the presence of vaccine attributable (either probably or definitely) systemic grade 3 or 4 toxicities or grade 4 local/skin toxicities in  $\geq 20\%$  of patients in the study. Patients will be withdrawn from study if they manifest Grade 3 or 4 systemic toxicity attributable to vaccination with TA-CIN or grade 4 local/skin toxicities attributable to vaccination with TA-CIN. In the event of two identical unexpected treatment-related Grade 4 toxicities, accrual will be suspended pending further review.

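### Section 7 and Section 7.1.1 give opposite answers on whether a silent, untreated grade 3-4 laboratory worsening is an adverse event, and nothing says which governs

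*Combined protocol and SAP*

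**What the plan says.** The laboratory paragraph of Section 7 sets its rule by grade. After study treatment, "all grade 3 and 4 clinical laboratory results that represent an increase in severity from baseline (pre-study) will be reported as adverse events". For lower grades, "A grade 1 or 2 clinical laboratory abnormality should be reported as an adverse event only if it is considered clinically significant by the investigator". Neither sentence asks about symptoms or therapy.

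Section 7.1.1, the formal definition of an AE, begins by counting "abnormal results of an investigation (e.g., laboratory findings, electrocardiogram" among the conditions that can be AEs. It ends with a different rule: "Abnormal laboratory values or test results constitute adverse events only if they induce clinical signs or symptoms or require therapy". That sentence makes no exception for grade 3-4.

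The term is then used in these places:

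- **Section 6.4**, as a condition for each further dose: "subjects must not have any acute grade 3 or higher hematologic and/or non-hematological adverse event that is judged possibly, probably or definitely related" to the vaccine or its administration.
- **Section 6.5**, on an unmet condition: "In the event that TA-CIN re-treatment criteria are not met, treatment may be delayed for up to 14 days".
- **Section 6.6**, which defines unacceptable toxicity through AEs ("or treatment-related grade 3 AEs not improving to" grade 2 or lower within two weeks is one limb) and adds "Exceptions include: Grade 3 lymphopenia". Section 6.9 makes an unacceptable AE a reason to end treatment.
- **Section 7.2**, which requires a causality judgement for AEs.
- **Section 11.3**, where the Medical Expert Committee receives a summary of AEs.
- **Section 12.5**, which tabulates AEs by type and grade.

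**The concern.** Safety is the primary objective in Section 2.1, and the AE is the unit in which most of it is recorded. If silent grade 3-4 laboratory changes can be in or out depending on which page is followed, the 12.5 table has no single definition, and the committee that may halt the study could see an incomplete summary.

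Dosing is also involved. The AE clause in 6.4 needs two things: that the result is an AE, and that it is judged at least possibly related. A result classed as a non-AE fails the first, and under 7.2 no causality judgement is required for it. A patient could then receive dose 2 or 3 when the Section 7 rule would have withheld it.

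**Working it through.** The plan states no figure on this point, so the check is a comparison of the two rules, followed by tracing where the answer is used.

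**Step 1. Apply both rules to each kind of post-treatment laboratory result (worse than baseline).**

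| Result | Section 7 | 7.1.1, last sentence | Agree? |
|---|---|---|---|
| Grade 3-4, symptomatic or treated | AE | Condition met | Yes |
| Grade 3-4, silent and untreated | AE | Not an AE | **No** |
| Grade 1-2, judged clinically significant, silent and untreated | Reportable | Not an AE | **No** |
| Grade 1-2, not judged clinically significant, symptomatic or treated | Not an AE | Condition met | **Different test** |
| Grade 1-2, not judged clinically significant, silent and untreated | Not an AE | Not an AE | Yes |

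The second row is the important one. Both sentences are current text, both are specific to laboratory results, and no sentence ranks them.

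**Step 2. Ask which rule was meant.** Four features point to Section 7:

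- its wording is mandatory for grade 3-4;
- the opening of 7.1.1 itself lists laboratory findings;
- 6.4 speaks of hematologic AEs;
- 6.6 exempts grade 3 lymphopenia, which would do little if silent laboratory results were never AEs.

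This supports an inference about intent. It does not remove the contrary sentence.

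**Step 3. Trace one silent, untreated grade 3-4 worsening judged possibly related.**

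- *12.5 table and Medical Expert Committee summary:* included under Section 7, omitted under 7.1.1.
- *6.4 AE clause:* triggered under Section 7, not under 7.1.1.
- *6.4 numeric limits:* these apply whether or not the result is an AE. They cover white cells, lymphocytes, neutrophils, platelets, hemoglobin, total bilirubin, AST/ALT and creatinine. They do not cover other measured tests such as sodium, potassium, calcium, glucose or magnesium (Section 10, footnote 9).
- *Recovered values:* a listed test that returns within its limit during the 14-day delay in 6.5 passes the numeric check again. The AE clause states no recovery provision, so AE status still decides if that clause is read as written.

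**Step 4. Scale.** With 7-8 patients per site group and 15 in total (Section 12.4), one patient is 1/7 = 14.3% or 1/8 = 12.5% of a group, and 1/15 = 6.7% of the study. This is the weight of one case, not a forecast of how many there will be.

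**The case against.** The strongest reply is that 7.1.1 contains a leftover sentence and that any experienced site would follow the grade-based rule in Section 7. The textual evidence for that intent is good. Central procedures would also help: the Coordinating Center sets AE documentation procedures, case report forms are reviewed centrally, and safety meetings are weekly. Divergence between sites is therefore a possibility, not a finding. What remains is that the definition a site would consult says the opposite of the reporting rule.

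The backstops are real. Section 6.6 withdraws patients with grade 3-4 systemic toxicity attributable to the vaccine. It says toxicity, not AE, so 7.1.1 does not plainly disable it. The stopping rule in the preceding sentence is confined to probable or definite attribution; the withdrawal sentence states no level. If that limit does not carry over, withdrawal closes most of the dosing gap. If it does, the gap is mainly results judged only possibly related, which 6.4 covers and 6.6 would not. Section 6.9 also allows the investigator to stop treatment.

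A reader might infer more than the documents support:

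- *That 12.5 is the only safety analysis.* It is not. Section 11.3 plans a toxicity review every six months by the data safety monitoring board, and 12.4 has an SAE stopping rule. SAEs are defined separately in 7.1.2, so the 12.4 rule does not depend on this conflict.
- *That the 6.6 stopping rule would be missed.* Its limit is 0.20 × 15 = 3 patients, and losing one leaves 2/15 = 13.3%. That requires reading toxicities as AEs, a systemic event, probable or definite attribution, and a count exactly at the limit.
- *That counts of tests or decisions measure the effect.* Footnotes 9 and 10 name 16 + 4 = 20 tests, of which 7 have a 6.4 limit and 13 do not, and there are 2 × 15 = 30 planned re-dosing decisions. These describe where the question could arise. The documents do not reproduce the CTCAE thresholds, so they do not show which of the 13 can reach grade 3-4.

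**Conclusion.** The conflict is real and should be corrected. For silent, untreated grade 3-4 laboratory worsening the two rules cannot both be followed, and for grade 1-2 results they use different tests. Section 7 is very probably the intended rule.

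Following 7.1.1 literally would certainly remove such results from the 12.5 table and the Medical Expert Committee's AE summary. The dosing consequence is narrower. It concerns a related result whose test has no 6.4 limit or has recovered, and which neither the 6.6 withdrawal sentence nor investigator judgement catches. It also assumes that the 6.4 clause applies as written, without an implied recovery provision.

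The documents give no rate of silent grade 3-4 results, so the number of patients affected cannot be estimated.

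**What to change.** **Section 7.1.1.** Replace the last sentence with two rules:

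1. After study treatment, laboratory abnormalities are AEs as set out in the laboratory paragraph of Section 7: every grade 3-4 result worse than baseline, and a grade 1-2 result only on the investigator's judgement of clinical significance.
2. For other abnormal test results, such as an electrocardiogram, the present symptom-or-therapy criterion stays.

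The post-treatment limit and the second rule are both needed. Without them the change would widen the period covered or leave non-laboratory tests without a specific criterion.

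**Section 6.4.** At the same time, state whether the grade 3 lymphopenia exception in 6.6 also applies to re-dosing. This is a separate but related gap. As written, 6.4 has no such exception, so once laboratory results clearly count as AEs, a related grade 3 lymphopenia could bar further doses even after the count is back above the 6.4 limit of 500.

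**Cost.** The change needs two sentences in 7.1.1 and one in 6.4, with no new visits, samples or patients. Somewhat more laboratory AEs will be listed, and a few doses may be withheld.
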